7.4.7 Adverse Event

7.4.7.1 Definition of Adverse Event

An adverse event (AE) is any unfavorable and unintended sign (including a clinically significant abnormal laboratory finding, for example), symptom, or disease temporally associated with the use of a medicinal product, whether or not considered related to the medicinal product. Clinical signs and symptoms of rosacea: erythema, telangiectasia, burning, dryness, scaling/peeling and pruritus are considered as part of the baseline dermatological history. If a new rosacea sign or symptom or worsening of a rosacea sign or symptom is believed by the investigator to be related to the study drug and not the disease, then it should also be recorded as an AE.

At each visit, the study site personnel will question the subject about adverse events using an open question taking care not to influence the subject's answers, e.g., "Have you had any problems since your last visit?"

Any adverse event, whether or not it is related to the test products, will be reported on the source document and eCRF along with the date of onset, the severity, the relationship to the test product and the outcome. Under certain circumstances, additional information may be requested.

When an adverse event persists at the end of the study, the Investigator will ensure a follow-up of the subject until the Investigator/CRO/Sponsor agree that the event is satisfactorily resolved or that no further follow-up is required.

CONFIDENTIAL

Version Date: 07 March 2017

7.4.7.2 Severity and Relationship of Adverse Event to Study Drug

The severity of an adverse event is to be scored according to the following scale:

1	Mild	Awareness of sign or symptom, but easily tolerated
2	Moderate	Moderate Discomfort enough to cause interference with usual activity
3	Severe	Severe Incapacitation with inability to work or perform usual activity

The relationship of an adverse event to study drug is to be assessed according to the following definitions:

- Not Related – no temporal association or the cause of the event has been identified, or the drug cannot be implicated based upon available information.
- Possibly Related – temporal association, but other etiologies are likely to be the cause. However, involvement of the drug cannot be excluded, based upon available information.
- Definitely Related – established temporal or other association (e.g., re-challenge) and event is not reasonably explained by the subject's known clinical state or any other factor, based on available information.

7.4.8 Serious Adverse Event

A serious adverse event (SAE) is an adverse event (AE) or suspected adverse reaction (SAR) that, in the view of either the investigator or sponsor, results in any of the following outcomes:

- Death;
- A life-threatening adverse event or life-threatening suspected adverse reaction, (the term "life-threatening" in the definition of "serious" refers to an event or suspected adverse reaction in which in the view of either the investigator or sponsor, its occurrence places the patient or subject at risk of death . It does not include an adverse event or suspected adverse reaction that, had it occurred in a more severe form, might have caused death;
- Inpatient hospitalization or prolongation of existing hospitalization;
- Persistent or significant incapacity or substantial disruption of the ability to conduct normal life functions; or
- A congenital anomaly/birth defect.

Important medical events that may not result in death, be life-threatening, or require hospitalization may be considered a serious when, based upon appropriate medical judgment, they may jeopardize the patient or subject and may require medical or surgical intervention to prevent one of the outcomes listed in the serious definition above. Examples of such medical events include allergic bronchospasm requiring intensive

CONFIDENTIAL

Version Date: 07 March 2017

treatment in an emergency room or at home, blood dyscrasias or convulsions that do not result in inpatient hospitalization, or the development of drug dependency or drug abuse.

The Investigator or designee must report any SAE occurring in a subject receiving study medication to the Medical Monitor immediately (within 24 hours (1 business day) of becoming aware of the event), even if the SAE does not appear to be drug-related. This should be done by telephone and/or by sending a copy of the Serious Adverse Event form (via fax or email pdf copy) plus other supporting documentation, as required. SAE forms should be sent to:

[REDACTED]

All additional follow-up evaluations must also be reported as soon as possible. All SAEs will be followed until the CRO/Sponsor agrees that the event is satisfactorily resolved or that no further follow-up is required.

The CRO/Sponsor will be responsible for notifying the relevant authorities of any SAE according to applicable regulations. The CRO/Sponsor will also ensure that any central IRB/IEC and any other participating Investigators are notified of the SAE, as required. The PI is responsible for ensuring that their local IRB/IEC, if applicable, is notified of the SAE, as per the IRB/IEC standard operating procedures.

Serious Adverse Events must be reported immediately to the appropriate medical monitor as listed below:

Medical Monitors:

[REDACTED]

7.5 TEST MATERIALS

7.5.1 Administration

Study drug will be applied by the subject to the entire area of the face, once daily, preferably in the morning, for a period of up to 12 months (52 Weeks \pm 14 days) after performing the first application of study drug at the study site, under the supervision of the study coordinator or designee to ensure the subject understands the treatment application instructions (see Appendix A, Instructions on Application of Study Drug). The subject will be provided a copy of the Instructions on Application of Study Drug. Once the subject has read the instructions and demonstrated proficiency in application at the study site, subjects will continue daily treatment application, each morning, during the treatment period, in an outpatient setting.

Subjects will be instructed to wash their face prior to application of the study drug. The study drug is packaged in a tube. The cap of the tube should be removed and a thin layer of the gel should be applied to the entire face, avoiding contact with the eyes, mouth and inside the nose. The dose applied will be applied as a thin layer, each day, preferably in the morning

At the Baseline visit and Months 3, 6 and 9 visits, subjects will be dispensed three or four tubes of study drug. Each tube contains enough study drug for 4 weeks of treatment. Prior to application of study drug, the subject number and date of dispensing should be recorded on the tube and the tube weighed. The tube weights will be recorded on the appropriate source document. When the used tubes are returned at the next visit, the tubes will be weighed again, and the weight will be recorded. At each visit, the subject's diary should be reviewed to determine if they missed any applications since the last visit. Reported missed applications should be recorded in the eCRF. In addition, the date of the last application should be collected. At each visit the tubes will be weighed to confirm product use. All tube weighing will be done with the cap in place.

7.5.2 Products Identity

Omiganan Topical gel [REDACTED] in this protocol, in previously conducted phase 1 and 2 clinical studies, and in other historical documentation is based on the concentration of omiganan pentahydrochloride. The product concentration based on the active moiety is omiganan topical gel [REDACTED]. To be consistent with the naming convention in pre-existing documents, the nomenclature concentration of omiganan [REDACTED] will be referred to in this protocol and associated clinical and non-clinical documents.

CONFIDENTIAL

Version Date: 07 March 2017

Further, in order to comply with USP General Chapter <1121> Nomenclature to express the strength of the drug product based upon the active moiety, the strength of the omiganan product will be recorded on the clinical supplies documentation for phase 3 studies as Omiganan topical gel, [REDACTED]

[REDACTED]	[REDACTED]
[REDACTED]	[REDACTED]
[REDACTED]	[REDACTED]
[REDACTED]	[REDACTED]
[REDACTED]	[REDACTED]
[REDACTED]	[REDACTED]
[REDACTED]	[REDACTED]
[REDACTED]	[REDACTED]
[REDACTED]	[REDACTED]
[REDACTED]	[REDACTED]

7.5.3 Packaging

Study drug will be provided in 20-gram tubes. Drug supplies will be packaged as bulk supplies.

7.5.4 Labeling

The requirements for drug product labeling will comply with the Regulations of the country where the clinical trial will be conducted.

7.5.5 Subject Dosing and Use Instructions

Under the supervision of the study coordinator or designee, the first dose of study drug will be applied by the subject, as a means of educating subjects in the proper technique for applying the study drug (see Appendix A for instruction on applying the drug). After the initial onsite instruction and treatment application, subjects will apply the dose each day, preferably in the morning, in an outpatient setting.

7.5.6 Treatment Compliance

Subjects should not miss ANY visits to the study site for status assessments. Study drug treatment compliance will be assessed by reviewing the subject's diary for any missed applications since the last visit or based on subject reported information on missed

applications in the event of a lost diary. Subjects should be applying the topical gel each day during the study treatment period.

7.5.7 Dispensing and Return of Study Product

The first dose of study drug will be applied at the study site. Subjects will be instructed on the proper procedure for study drug application for subsequent doses. For use in the outpatient setting, three or four tubes of study drug will be dispensed to each subject at the study visits at Baseline (4 tubes), Month 3 (3 tubes), 6 (4 tubes) and 9 (3 tubes) visits.

When a new tube of study drug is dispensed, study personnel must record the date dispensed and subject number on the labels. The dispensing information must be recorded in the source document.

The subject will be instructed to return the tubes of study drug at each study visit (Months 1, 3, 6, 9 and 12) to check compliance. At the Month 3, 6 and 9 Visit, the used tubes will be exchanged for three or four new tubes of study drug. Additional tubes are available for dispensing in the event that tubes are lost or damaged.

Tubes should be weighed prior to dispensing to the subject and again after the subject returns the tube to the clinical study site. The weight of the tube should be recorded to the nearest tenth of a gram. Tubes should be weighed with the cap on.

7.5.8 Accountability

In accordance with local country regulations, the Investigator must agree to keep all clinical supplies in a secure location with restricted access.

Upon receipt of the clinical supplies, the Investigator or designee will conduct a complete inventory of all test materials and assume responsibility for storage and dispensing. Dispensation and return of test material must be appropriately documented. Under no circumstance should any of the clinical supplies sent to the Investigator be used in any unauthorized manner.

All used and unused clinical supplies will be appropriately inventoried and returned to the designated facility as specified by the Sponsor.

7.5.9 Prior and Concomitant Therapy

Therapies used within one month prior to the Baseline visit should be recorded on the Previous/Concomitant Therapy Form of the CRF. Washout medications should be listed on the Previous/Concomitant Therapy Form, when applicable. Rosacea treatments used in the last 5 years should be recorded.

CONFIDENTIAL

Version Date: 07 March 2017

Any therapy used by the subject either at or following the Baseline visit through study completion will be considered concomitant therapy; e.g., aspirin, Tylenol, birth control pills, vitamins, etc. Every attempt should be made to keep concomitant therapy dosing constant during the study. Any change to concomitant therapy should be noted on the Previous/Concomitant Therapy page in the eCRF.

An Adverse Event should be recorded for any subject starting a concomitant therapy (except therapies used as prophylaxis) to treat any health condition/event not identified in the subject's medical history.

Subjects should wash their face 15 minutes prior to study drug applications. Subjects must adhere to the study instructions during the treatment period starting in the morning of Day 1. The instructions include the following:

- Wait until study gel is dry before applying makeup.
- No new lotions, gels, powders, moisturizers, etc., are to be used on the skin in the treatment areas. A bland moisturizer may be used throughout the study. All makeup, approved lotions, moisturizers, etc. and sunscreen should be applied after study gel is dry.

7.5.9.1 Excluded Concomitant Therapy

No other rosacea treatment, other than the study drug, will be permitted. Interfering concomitant therapies include those listed below:

Interfering Topical Therapies (on the face)

- Abradants, astringents, toners, facials, masks, washes, or medicated facial cleansers
- Tanning booths/beds, sunbathing, excessive exposure to the sun (tanning is not permitted)
- Antibiotics other than topical ocular application
- Antimicrobial soaps
- Corticosteroids
- Other anti-inflammatory drugs
- Retinoids
- Other acne or rosacea treatments (e.g., benzoyl peroxide, alphahydroxy acids, salicylic acid, azelaic acid, or metronidazole)

Interfering Systemic Therapies

- Antibiotics
- Corticosteroids
- Other acne or rosacea treatments (including oral retinoids or therapeutic vitamin A supplements)

CONFIDENTIAL

Version Date: 07 March 2017

- Change in dose, initiation and/or discontinuation of estrogen therapy (e.g., Gynogen, Valergen, Depo-Testadiol, Depogen, birth control pills)

7.6 STATISTICAL METHODS PLANNED

7.6.1 General Considerations

The statistical methods for this study are descriptive only. No hypothesis testing will be performed.

7.6.2 Sample Size Determination

The sample size for this study is based upon ICH E1a.

7.6.3 Randomization

This study is not randomized. Subjects providing written informed consent and having met all inclusion and exclusion criteria will be enrolled in the study.

7.6.4 Analysis Population

The “All-treated” analysis population will consist of all subjects receiving at least one application of study medication. All analyses will be performed on the all-treated population.

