Omiganan pentahydrochloride topical gel has been evaluated in over 2,500 people in human clinical studies at concentrations of 0.5%, 1.0%, 2.5% and 3% in Phase 1 studies; at concentrations of 1.0%, 1.75% and 2.5% in Phase 2 studies; and at concentrations of 1.0% in a Phase 3 study. Omiganan topical solution for acne has been evaluated at concentrations of 1.0% and 5% in Phase 1 studies, as well as 1.25%, 2.5% and 5% in Phase 2 studies. In these studies, including two Phase 2 studies of omiganan topical gel applied to the face of subjects with moderate to severe papulopustular rosacea, omiganan was found to be safe, and well tolerated. In the most recent Phase 2 study in which vehicle or omiganan pentahydrochloride topical gel 1.0%, 1.75% or 2.5% was applied once daily to the face of 240 moderate to severe rosacea subjects for 12 weeks, the most frequently reported adverse events were headache, sinusitis, and upper respiratory tract infections. Most treatment emergent adverse events were considered mild or moderate in severity.

Additionally, the systemic absorption of omiganan pentahydrochloride topical gel was evaluated at concentrations of 0.5%, 1%, 2.5% and 3%. Omiganan was not systemically absorbed when applied to the skin at concentrations ranging from 0.5% to 3% topical gel. In the most recent maximum use PK study of omiganan pentahydrochloride topical gel 2.5% w/w, applied for 21 days to the face of 26 subjects with moderate to severe papulopustular rosacea, no systemic absorption was detected. The results of the clinical studies and the safety data collected during the clinical studies of omiganan are summarized in the Investigator's Brochure.

Omiganan Topical gel [REDACTED] in this protocol, in previously conducted phase 1 and 2 clinical studies, and in other historical documentation is based on the concentration of omiganan pentahydrochloride. The product concentration based on the active moiety is omiganan topical gel [REDACTED]. To be consistent with the naming convention in pre-existing documents, the nomenclature concentration of omiganan [REDACTED] will be referred to in this protocol and associated clinical and non-clinical documents.

[REDACTED]

Further, in order to comply with USP General Chapter <1121> Nomenclature to express the strength of the drug product based upon the active moiety, [REDACTED]

[REDACTED]

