7.2.3 Withdrawal from Study Criteria

Reasons for discontinuation of study medication include, but are not limited to, the following:

- Adverse Event
- Pregnancy

- Withdrawal By Subject
- Lost To Follow-Up. The Investigator will try to reach the subject, twice by telephone (document telephone calls) and once by certified letter, before considering the subject lost-to-follow-up. The lost to follow-up discontinuation will be reported on the appropriate eCRF, and a copy of the letter sent to the subject will be maintained in the Investigator's file.
- Study Terminated By Sponsor
- Physician Decision
- Non-Compliance with Study
- Other

All premature discontinuations of study medication must be documented by the Investigator on the eCRF, and if due to an adverse event, on the Adverse Event Case Report page of the eCRF. All subjects should attempt to complete all visits and evaluations.

Subjects not completing the entire study should be fully evaluated (i.e., final visit procedures performed). All subjects are free to withdraw from participating in this study at any time and for whatever reason, specified or unspecified, and without prejudice to his or her medical care by a physician.

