7.3.3 Investigator Assessment

7.3.3.1 Investigators Global Assessment (IGA)

This is not an efficacy study, and therefore the Investigators Global Assessment is done for informational purposes. The evaluations should be performed by the Principal Investigator or appropriately qualified Sub-Investigator at each visit. **It is important that the same evaluator performs the evaluations for the same subject at each visit, however it may not be feasible in all instances. Every effort should be made to maintain consistency of the evaluator for each subject.**

CONFIDENTIAL

Version Date: 07 March 2017

The IGA is intended for the global evaluation of papulopustular rosacea. Background non-transient erythema and telangiectasias should not be assessed as part of the IGA. The IGA score represents the subject's condition at the time of the evaluation.

The following categories will be used from the IGA scale to perform the global evaluation of papulopustular rosacea:

Investigators Global Assessment (IGA) Scale

Grade	Grading Scale Score	Description of Papulopustular Rosacea Disease Status
Clear	0	No inflammatory papules or pustules.
Almost clear	1	Very few with 1 or 2 inflammatory papules/pustules.
Mild	2	Several (3-10) small inflammatory papules/pustules.
Moderate	3	11 to 19 small or large inflammatory papules/pustules and no nodules.
Severe	4	Numerous (≥ 20) small and or large inflammatory papules/pustules, and up to 2 nodules, (at baseline).

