7.6.6.1 IGA Summary

The IGA will be summarized across the study duration in order to evaluate safety as it pertains to the underlying condition of papulopustular rosacea.

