#### **4.2 Study Populations**

The “All-treated” analysis population will consist of all subjects receiving at least one application of study medication. All safety analyses will be performed on the all-treated population.

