#### **5.2 Missing Data**

Data will be handled on an observed case basis with no imputation..

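### The by-visit IGA summary pools grades recorded after interfering therapy was started, or after omiganan was stopped, with grades recorded on omiganan alone

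*Protocol*

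**What the plan says.** There is one analysis set. Protocol 7.6.4 defines it as everyone with at least one application and adds "All analyses will be performed on the all-treated population". SAP 4.2 agrees: "All safety analyses will be performed on the all-treated population". SAP 5.2 sets the missing-data rule: "Data will be handled on an observed case basis with no imputation".

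The IGA has a stated purpose in that set. Protocol 7.6.6.1, repeated in SAP 4.3.2, reads "The IGA will be summarized across the study duration in order to evaluate safety as it pertains to the underlying condition of papulopustular rosacea". Protocol 7.3.3.1 limits its standing: "This is not an efficacy study, and therefore the Investigators Global Assessment is done for informational purposes".

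On other treatment, Protocol 7.5.9.1 says "No other rosacea treatment, other than the study drug, will be permitted". It lists interfering topical and systemic therapies, including systemic antibiotics, systemic corticosteroids and oral retinoids.

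Protocol 7.2.3 gives an open-ended list of reasons for stopping study medication. Non-compliance is on it, but use of an interfering therapy is not named. The same section says "All subjects should attempt to complete all visits and evaluations".

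Therapy changes go on the eCRF (Protocol 7.5.9), the date of last application is collected (Protocol 7.5.1), and SAP 4.3.1 plans a summary of medication used before and during the study.

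**The concern.** Every subject enters with IGA grade 4 and may use no other rosacea drug for up to 12 months. Some use of interfering therapy is plausible. Protocol 5.1 describes treatments for severe rosacea as inadequate and reports growing use of isotretinoin. It also says that in the 12-week Phase 2 study "the most frequently reported adverse events were headache, sinusitis, and upper respiratory tract infections", and some of these infections may be treated with antibiotics.

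If such a subject stays in the study, the later grades reflect omiganan plus another drug, or the other drug alone. The IGA table reports them in the same row as grades on omiganan alone. Where the added drug works, a subject whose disease was poorly controlled is counted as improved. That undercuts the purpose the plan gives the table, and with no comparator arm nothing in the study helps a reader to see it.

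**Working it through.** **No plan figure to reproduce.** The targets of 300 and 100 subjects are exposure counts taken from guidance. The documents give neither a rate of interfering-therapy use nor an expected IGA distribution. The check is therefore a trace through the rules, followed by an illustration on stated assumptions.

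**Step 1: trace one subject.** Take a subject at grade 4 at Month 3 who then starts an oral rosacea drug and is grade 2 at Month 6.

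- *In the analysis set?* Yes; one application is enough (Protocol 7.6.4, SAP 4.2).
- *Month 6 grade used?* Yes; it is an observed value at a scheduled visit (SAP 5.1, 5.2).
- *Marked or separated?* No. Neither document has an on-treatment set, a flag, a deviation rule or a cut-off.
- *Worsening recorded as an adverse event?* Under Protocol 7.4.7.1, only if the investigator attributes it to study drug rather than to the disease.
- *New drug triggers an adverse event?* Not under Protocol 7.5.9, which requires one only when the condition treated is absent from the medical history. Rosacea history is taken for every subject at Screening. An antibiotic for new sinusitis would trigger one.
- *Leaves the study?* Not settled. Protocol 7.2.3 does not tie use of an interfering therapy to stopping.
- *Flare visible elsewhere?* An IGA taken at an unscheduled visit is listed but not summarised (SAP 5.3).
- *Drug visible elsewhere?* Yes, in the SAP 4.3.1 medication summary, but with no stated breakdown by the 7.5.9.1 classes and no link to visit or IGA grade.

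**Step 2: effect on the proportion at IGA 0 or 1.** Let f be the share of observed subjects who have started such therapy, p0 the proportion at IGA 0 or 1 on omiganan alone, and p1 the proportion among those with the other therapy.

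Reported = (1 − f) × p0 + f × p1, so shift = f × (p1 − p0).

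Assume p0 = 30%. For example, with f = 10% and p1 = 70%: 0.90 × 30 + 0.10 × 70 = 27 + 7 = 34%.

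| f | p1 = 30% | p1 = 50% | p1 = 70% |
|---|---|---|---|
| 5% | 30% | 31% | 32% |
| 10% | 30% | 32% | 34% |
| 20% | 30% | 34% | 38% |
| 30% | 30% | 36% | 42% |

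The shift runs from 0 to 12 points. It is negative if p1 is below p0. It compares the pooled figure with subjects on omiganan alone, not with what the users would have scored untreated, which cannot be observed.

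**Step 3: effect on the proportion at grade 4.** Assume 200 subjects seen, 60 (30%) at grade 4 without other therapy, and use unrelated to grade. Even if every grade 4 user improves, the reported proportion is 30% × (1 − f):

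- f = 5%: 57/200 = 28.5%
- f = 10%: 54/200 = 27%
- f = 20%: 48/200 = 24%

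These are the largest falls under that assumption. A larger fall needs use to be concentrated among grade 4 subjects.

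**The case against.** The all-treated set is the right one for adverse events and exposure, and nothing here argues for replacing it. The IGA is informational and nothing is tested. Grade 4 is both the entry grade and the top of the scale, so the table cannot show worsening beyond baseline; what is distorted is mainly apparent improvement, which the study does not claim to establish. All of this stands and limits the weight of the point. It does not remove it, because the plan still uses the IGA to judge safety for the underlying disease.

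Three stronger readings are tempting, and the documents do not support them.

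- A reader might infer that the distortion always favours omiganan. The 7.5.9.1 list also contains tanning and sun exposure, toners and topical corticosteroids, and Protocol 5.1 names sun, some skin care products and prolonged topical steroid use as triggers or possible causes. Direction depends on the class.
- A reader might infer that no planned output shows the use of these drugs. SAP 4.3.1 does; what is missing is separation by class and a link to the IGA.
- A reader might infer that each percentage point of use takes a full point off grade 4. That requires every user to be otherwise at grade 4 and to improve, and the documents link use to grade nowhere.

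It is also fair that a site may withdraw such a subject for non-compliance. Later grades then leave the observed-case table, which is a dropout question and not this one. Since Protocol 7.2.3 leaves this open, sites may differ.

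**Conclusion.** The point holds for the IGA display alone. Both documents pool grades recorded after interfering therapy, or off study drug, with grades on omiganan alone. Where the therapy is effective, poor control can be shown as improvement, and the adverse event rules may not capture it.

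The size cannot be derived from the documents. It is zero if no one uses such therapy and stays in, or if the therapy does not change the IGA. Under the assumed rates above it reaches 12 points in IGA 0 or 1. The weight is modest: the study is descriptive and the IGA informational. The case for acting is that the data are already collected and the change is cheap. A reader might extend the concern to the adverse event tables, but nothing in the documents shows a defect there.

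**What to change.** In SAP 4.3.2:

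1. Keep the all-treated IGA table by visit, with all observed subjects in the denominator. Show as separate rows those who have started another rosacea treatment (which in 7.5.9.1 includes oral retinoids), those who have started another systemic therapy on the 7.5.9.1 list, and those off study drug. State the order of precedence when a subject fits more than one row, and whether a subject returns to the main rows after a short course ends.
2. Add a count of subjects starting each 7.5.9.1 class, with other rosacea treatment shown separately.
3. Optionally, add an IGA summary restricted to visits before the first interfering therapy, as a sensitivity display. State beside it that it removes poorly controlled subjects and so can look better than the full set.

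Protocol 7.2.3 and 7.5.9.1 should be reconciled on the status of a subject who takes an interfering therapy. Which rule applies is for the sponsor to decide.

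The cost is SAP wording, extra rows in one table, one short count table and some coding of medications to class. Therapy changes and last application dates are already collected. Some rows will hold few subjects.
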